11.2. ADVERSE EVENTS – SEVERITY RATING

The severity of each AE should be characterized and then classified into one of three clearly defined categories as follows:

- Mild – the AE does not interfere in a significant manner with the subject's normal functioning level. It may be an annoyance.
- Moderate – the AE produces some impairment of functioning but is not hazardous to health. It is uncomfortable or an embarrassment.
- Severe – the AE produces significant impairment of functioning or incapacitation and is a definite hazard to the subject's health.

These three categories are based on the Investigator's clinical judgment, which in turn depends on consideration of various factors such as the subject's report and the physician's observations. The severity of the AE should be recorded in the appropriate section of the EDC.

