# 6.1.6. Data Adjustments/Handling/Conventions

[figure not shown]
Only limited data required for analysis will be presented in listings or Clinical Data Interchange Standards Consortium (CDISC) datasets. Analysis results will be presented and summarized in either tables and/or listings. Data not subject to analysis according to this plan will not appear in any tables and listings.

The version 24.0 of the Medical Dictionary for Regulatory Activities (MedDRA) will be used to classify all AEs by system organ class (SOC) and preferred term (PT).

Ongoing AEs from the pivotal studies will be classified as TEAEs in the current study only if they increase in severity on or after the date of the first dose of study drug in the current study. Otherwise, they will be classified as medical history events.

Adverse events with entirely missing start dates will be classified as treatment-emergent, as appropriate.

For partial AE start dates: (a) if only the day is missing, and the month and year match the first dose date and the end date is on or after the first dose date, or AE is ongoing, then the date is assigned the first dose date thus the event will be considered as treatment-emergent; if the month and/or year do not match the first dose date or the end date is prior to the first dose date, then the day is assigned the first day of the month (01); (b) if month or the day and month are missing, and the year matches the first dose date and the end date is on or after the first dose date, or AE is ongoing, then the date is assigned the first dose date; if the year does not match the first dose date

or the end date is prior to the first dose date, then the day/month are assigned the first day of the year (01JAN).

For partial end dates: (a) if only the day is missing, then the day is assigned the last day of the month; (b) if both day and month are missing, they are assigned the last day of the year (31DEC).

Participants will be analyzed by the treatment received for all safety and tolerability assessments.

A treatment related AE is any AE with a relationship to the study drug of "Possibly Related" or "Probably Related" or "Reasonable Possibility".

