#### 9.1. Adverse Events

An AE is any undesirable event that occurs to a participant during a study, whether that event is considered related to Study Drug.

All summaries of AEs will be based on treatment-emergent adverse events (TEAEs) unless specified otherwise.

An adverse event is considered a TEAE if:

• The adverse event first occurred on or after the date of the first dose of study drug; or

• The adverse event was before the date of the first dose of study drug, but it increased in severity or became serious on or after the date of the first dose of study drug.

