#### 9.1.4. Summaries of Adverse Events

An overall summary of TEAEs will be provided by treatment. This summary will present number and percentage of participants with TEAEs per the following classifications:

- Participants with any TEAEs
- Participants with Treatment-Emergent Drug-Related AEs
- Participants with Treatment-Emergent AEs by Maximum Severity as Mild, Moderate, and Severe.
- Participants with TEAE leading to discontinuation from study
- Participants with Treatment-Emergent SAEs
- Participants with Treatment-Emergent SAEs leading to discontinuation from study
- Participants with Treatment-Emergent SAEs resulting in death

The following summary tables for TEAEs will be presented:

- Number and percent of participants reporting treatment-emergent AEs, grouped by MedDRA system organ class and preferred term
- Number and percent of participants reporting treatment-emergent drug-related AEs, grouped by MedDRA system organ class, and preferred term
- Number and percent of participants reporting treatment-emergent AEs, grouped by MedDRA system organ class, preferred term, and maximum severity
- Number and percent of participants reporting treatment-emergent SAEs will be tabulated by system organ class and preferred term and presented by treatment.
- Number and percent of participants reporting treatment-emergent AEs leading to study discontinuation, grouped by MedDRA system organ class and preferred term

For the summary tables above, the SOC terms and PTs will be presented in decreasing order of the total number of participants (frequency) who experienced each AE. System organ class terms and PTs with the same frequency will be presented alphabetically. In the case of multiple occurrences of the same TEAE within the same participant, each participant will only be counted once for each preferred term.

The following data listings for AEs will be provided for each participant by displaying the events captured on the CRF:

- All AEs,
- All serious AEs,
- All AEs leading to study discontinuation, and
- All AEs leading to Death.

In the AE data listings, all AEs will be displayed. AEs that are not treatment-emergent will be flagged in the AE listings.

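### The only specified death count is limited to treatment-emergent SAEs, so a death recorded on a carried-over event that was already serious, with no rise in recorded severity, is left out of it

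*SAP*

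**What the plan says.** SAP 9.1 sets the default: "All summaries of AEs will be based on treatment-emergent adverse events (TEAEs) unless specified otherwise". The overall summary in SAP 9.1.4 (Table 14.3.1.1) follows it, and its death row reads "Participants with Treatment-Emergent SAEs resulting in death". SAP Tables 2 and 3 plan no table of all deaths.

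Treatment-emergence is defined in two places.

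- SAP 9.1 has two limbs. The first is "The adverse event first occurred on or after the date of the first dose of study drug; or". The second covers events with earlier onset, which qualify if "it increased in severity or became serious on or after the date of the first dose of study drug".
- SAP 6.1.6 is narrower for rollover events: "Ongoing AEs from the pivotal studies will be classified as TEAEs in the current study only if they increase in severity". It then adds: "Otherwise, they will be classified as medical history events".

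Severity has three levels, mild, moderate and severe, in both Protocol 11.2 ("The severity of each AE should be characterized and then classified into one of three clearly defined categories") and SAP 9.1.1. There is no fatal grade. SAP 9.1.3 lists death among the outcomes that make an event serious.

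Two other outputs bear on deaths. SAP 9.1.4 plans a listing of fatal AEs (Table 14.3.2.3) and says that the AE listings show every AE, with a flag on those that are not treatment-emergent. SAP 7.1 tabulates reasons for discontinuation without naming the categories.

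**The concern.** Everyone in this study comes from a parent trial, so events that began before the first open-label dose are built into the design. Both SAP rules ask whether such an event got worse on a scale that ends at severe; 9.1 also asks whether it became serious. Neither asks whether the participant died of it. An event that was already serious at rollover cannot become serious again, and if its recorded severity stays the same it meets neither test.

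Long-term safety and tolerability is the only objective in SAP 2.1. SAP 10 drops the summaries of laboratory values, vital signs, ECG and C-SSRS, so the AE tables are nearly all the safety evidence that remains. For a record of this kind the omission can only lower the death count. Elsewhere the SAP leans the other way: a missing severity becomes severe, and a missing relationship becomes related.

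**Working it through.** The plan states no number of deaths, so there is no figure to reproduce. The check applies the two rules to every possible state of an event that began before first dose and ended in death after it.

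**States.** Severity after dosing is equal to or higher than severity at rollover. That gives 3 pairs starting from mild, 2 from moderate and 1 from severe: 3 + 2 + 1 = 6. Each event was either serious or not serious at rollover, so there are 6 × 2 = 12 states. Death makes the event serious after dosing in all 12 (SAP 9.1.3).

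**Rules.**

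- SAP 9.1: treatment-emergent if severity rose, or if the event was not serious at rollover (death then makes it become serious).
- SAP 6.1.6: treatment-emergent only if severity rose.

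**Results.**

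| State of the fatal carried-over event | Number of states | Counted under 9.1 | Counted under 6.1.6 |
|---|---|---|---|
| Severity rose, serious or not at rollover | 6 | yes | yes |
| Severity unchanged, not serious at rollover | 3 | yes | no |
| Severity unchanged, already serious at rollover | 3 | no | no |

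So 9.1 misses 3 of 12 states and 6.1.6 misses 6 of 12. These are counts of logical cases, not of participants, and they say nothing about frequency.

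The last line of the table is the point here. The two rules disagree on the second line, and that conflict needs resolving in its own right, but resolving it in either direction leaves the last line uncounted. For an event already severe at rollover, a rise in recorded severity is impossible. For a mild or moderate one, it depends on whether the site raises the grade.

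**Size per record.** SAP 3.3 gives 1,081 participants. One missed death is 1/1,081 = 0.09 percentage points; two would be 2/1,081 = 0.19, and five 5/1,081 = 0.46. The numbers two and five are illustrations only.

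**The case against.** The strongest reply is that the check looks only at the old record. Protocol 11.1 starts AE monitoring at dosing and counts the worsening of an existing condition as an AE, and Protocol 11.5 requires a death within 30 days of study drug to be reported within 24 hours. A site may therefore enter the fatal worsening or complication as a new AE with on-study onset, which meets the first limb of SAP 9.1 and is counted. This stands as a limit: the gap opens only when the fatal outcome is attached to the existing record and no new one is made. Nothing in either document requires a new record, so it does not close the gap.

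A reader might infer that these deaths disappear from the report. The documents do not support that. The listing of fatal AEs in SAP 9.1.4 carries no treatment-emergent restriction and flags the rest, and Table 14.1.1 covers all early terminations. Some doubt remains. SAP 6.1.6 makes the event medical history and keeps data not being analysed out of tables and listings; no medical-history listing is planned; Listing 16.2.7.1 is titled for treatment-emergent events; and death is not named as a disposition category. Nor is a listing a count.

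A reader might also infer that a material share of deaths is lost. That would need the number of participants entering with such events, their fatality, and the total deaths. The documents give none of these. Protocol exclusions 7 and 8 bar parent-trial SAEs, and ongoing AEs of moderate or severe grade, when judged a safety risk. Exclusions 10 and 11 bar clinically significant unstable illness and other conditions that may affect safety or completion. They rest on judgment, so they do not rule the case out, but they make it uncommon.

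Finally, the row is labelled accurately and does not claim to count all deaths. That is fair: the weakness is that no all-deaths count stands beside it.

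**Conclusion.** The point holds in a narrow form. A death recorded on a carried-over event that was already serious, with unchanged recorded severity, is not in the only death count that the SAP specifies, under either definition of treatment-emergence. For such a record one death is counted as none. The effect is 0.09 percentage points per missed death on 1,081 participants; the number of such deaths is unknown and probably small.

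The conclusion assumes that the site attaches the death to the existing record, and that disposition does not already give a complete death total, which cannot be checked because its categories are not stated. It does not show that the reported number is wrong by any particular amount. This is a cheap improvement worth making in a safety-only study, not evidence of a serious bias.

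**What to change.** In SAP 9.1.4 and Table 14.3.1.1, add a row for all deaths from the first open-label dose through a stated end of follow-up, regardless of the onset date or treatment-emergent status of the causal event. The 30 days after study drug in Protocol 11.5 is one window already in the documents. Keep the present row beneath it as a sub-row.

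In SAP 6.1.6 and 9.1, state that a carried-over event with a fatal outcome after first dose is not reclassified as medical history and is shown in Table 14.3.2.3.

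The cost is one table row and a sentence in each of the two sections. The documents do not show which death fields the EDC holds, so the data source for the row should be confirmed and named. The drawback is that the count may be slightly higher and will include deaths from conditions that predate the extension; the sub-row lets the reader separate them.

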# 10. Changes from Planned Analyses

Due to the early sponsor termination of PTI-125-10, the following analyses will no longer be tabulated/listed:

- Mean change in clinical laboratory values from baseline to Weeks 4, 28 and 52
- Mean change in vital signs (blood pressure [supine], temperature, pulse rate) from baseline to Weeks 4, 16, 28, 40, and 52
- Mean change in body weight from baseline to Weeks 4, 16, 28, 40, and 52

- Shifts in physical exam (PE) findings from baseline to Weeks 4, 16, 28, 40, and 52
- Shifts in neurological exam (NE) findings from baseline to Week 4, 16, 28, 40, and 52
- Mean change in ECG parameters from baseline to Weeks 4, 28, and 52
- Concomitant medications/treatments usage
- Shifts in the C-SSRS from baseline to Weeks 4, 16, 28, 40, and 52.
- Shifts in HbA1c values from baseline to Weeks 28 and Week 52. The analysis is done separately among subjects who were previously on placebo and simufilam in PTI-125-06 and PTI-125-07 phase 3 studies.

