4. SUMMARY OF STUDY DESIGN

This is a multi-national, multi-center, fixed-dose, open-label extension study that will continue through FDA approval of simufilam or program termination ([Appendix A](#)). After completing participation in either PTI-125-06 or PTI-125-07, subjects will have the option to participate in this study. After the subject provides consent and the Investigator confirms the subject satisfies both inclusion and exclusion (I/E) criteria, the study drug will be administered at the research site on Study Day 1 and subsequent visits will be scheduled.

Subjects who already completed participation through Week 52 in PTI-125-10 will have the option to return to the study and continue participation. After the subject provides consent, the Investigator will confirm that the subject continues to satisfy both the I/E

criteria. The study drug will be administered at the research site on Re-entry Day 1 and subsequent visits will be scheduled. The length of their participation gap will dictate which visits apply to them.

We anticipate up to 1,350 subjects may enroll in this study. Approximately 170 clinical sites in the USA, Canada, the Republic of Korea, and Australia will have the option to participate in this collaborative research effort.

For subjects electing to participate, the clinical and laboratory assessments from the Week 76 (PTI-125-06) or Week 52 (PTI-125-07) End-of-Treatment visit will serve as Baseline Visit assessments for the open-label study on Study Day 1. Additional blood samples will be taken on Study Day 1 to assess Hemoglobin A1c (HbA1c) and plasma biomarkers upon receipt of required supplies. All subjects will return in 4 weeks and then every 12 weeks thereafter for safety assessments.

For subjects re-entering the study, the length of their participation gap will determine their need for clinical and laboratory assessments. A blood sample will be taken to assess HbA1c and plasma biomarkers upon receipt of required supplies.

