At all post-baseline visits, subjects will report any adverse events since their last visit. In addition to adverse event monitoring, safety will be evaluated by vital signs, brief examinations, clinical laboratory tests (biochemistry, hematology, and urinalysis) and the Columbia Suicide Severity Rating Scale (C-SSRS). Cognition and function will be monitored using the Clinical Dementia Rating (CDR) scale. Study drug use since the last visit will be assessed and a new bottle of study drug will be dispensed.

The emerging subject safety assessments from this study will be monitored on an ongoing basis by an independent Data Safety Monitoring Board (DSMB) throughout its duration.

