12.2. SAFETY ANALYSIS

Adverse events reported on CRFs will be mapped to preferred terms and organ systems using the MedDRA mapping system. Vital signs and clinical laboratory results will be descriptively summarized in terms of change from Study Day 1 values.

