# 2.2. Study Endpoints

#### 2.2.1. Safety Endpoints

The safety endpoints of this study include the following:

• Incidence of adverse events (AEs) including treatment-emergent, serious, related to study drug, and leading to withdrawal along with AEs by severity and relationship to study drug.

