# 9. Safety and Tolerability Analysis

All safety analyses will be performed on the safety analysis set.

Safety will be evaluated from reported AEs. No inferential statistical tests will be performed, unless otherwise specified.

For all safety and tolerability analyses, participants will be analyzed by the actual treatment.

All safety and tolerability data will be presented in listings.

[figure not shown]

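### SAP 10 drops the laboratory and vital-sign change summaries that Protocol 12.2 commits to, in a study whose only objective is safety, and the SAP contradicts itself on whether those data will be listed

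*SAP*

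**What the plan says.** Protocol 3 and SAP 2.1.1 state one objective: long-term safety and tolerability of the 100 mg tablets. Protocol 4 sets out how safety is judged: "In addition to adverse event monitoring, safety will be evaluated by vital signs, brief examinations, clinical laboratory tests", followed by the C-SSRS. Protocol 12.2 states the analysis: "Vital signs and clinical laboratory results will be descriptively summarized in terms of change from Study Day 1 values".

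SAP 10 says: "Due to the early sponsor termination of PTI-125-10, the following analyses will no longer be tabulated/listed". Nine items follow: laboratory values, vital signs, body weight, physical examination, neurological examination, ECG, concomitant medications, C-SSRS and HbA1c. SAP 2.2.1 leaves a single safety endpoint: "Incidence of adverse events (AEs) including treatment-emergent, serious, related to study drug, and leading to withdrawal", with adverse events also broken down by severity and relationship. SAP 9 bases the safety evaluation on reported adverse events.

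On listings the SAP points both ways. SAP 6.1.6 says "Only limited data required for analysis will be presented in listings or Clinical Data Interchange Standards Consortium (CDISC) datasets" and "Data not subject to analysis according to this plan will not appear in any tables and listings". SAP 9 says "All safety and tolerability data will be presented in listings", and SAP 12.3 adds that, as a rule, each CRF domain gets its own listing.

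**The concern.** The protocol treats measured safety data as part of the safety evaluation, over and above adverse events. As the SAP stands, the report would answer the study's one question from adverse events and disposition alone, and two data types with an explicit analysis commitment would not be summarised.

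Adverse events do not fully replace the measurements. Protocol 11.1 gives a laboratory or examination abnormality as an example of an adverse event when it is new and clinically significant. For liver tests, Protocol 7.1.9 asks the investigator to consider discontinuation; it does not require it. A measured abnormality that the investigator does not judge clinically significant therefore need not appear in any planned output. This matters more because Protocol 2.2 reports adverse liver findings in the six-month rat studies.

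**Working it through.** The plan gives no figure to reproduce: SAP 3.2 states that no sample size was calculated. The check compares the texts and counts items.

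**Step 1. What SAP 10 drops, against what the protocol promises.** Visits are those named in SAP 10.

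| Domain | Post-baseline visits dropped | Standing in the protocol |
|---|---|---|
| Laboratory | 3 (Weeks 4, 28, 52) | Summary promised in 12.2; named in 4 |
| Vital signs | 5 (Weeks 4, 16, 28, 40, 52) | Summary promised in 12.2; named in 4 |
| C-SSRS | 5 | Named in 4; no summary in 12.2 |
| Physical examination | 5 | Named in 4 (brief examinations); no summary in 12.2 |
| Neurological examination | 5 | Named in 4 (brief examinations); no summary in 12.2 |
| Weight | 5 | Scheduled in Appendix B; not in 4 or 12.2 |
| ECG | 3 | Scheduled in Appendix B; not in 4 or 12.2 |

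- Conflict with Protocol 12.2: 3 + 5 = 8 summaries.
- Named as safety measures in Protocol 4 only: 5 + 5 + 5 = 15.
- Scheduled only: 5 + 3 = 8.
- Total: 8 + 15 + 8 = 31.

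The other two of the nine items, concomitant medications and HbA1c, are outside this point.

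**Step 2. What remains.** Counting SAP Tables 2 to 4 by title:

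- Tables: 14.1.1, 14.1.2 and 14.3.1.1 to 14.3.1.6, so 2 + 6 = 8.
- Listings: 14.3.2.1 to 14.3.2.3, plus 16.2.1.1, 16.2.4.1 and 16.2.7.1, so 3 + 3 = 6.
- Total: 8 + 6 = 14. All concern disposition, demographics and baseline, or adverse events. Outputs titled for post-baseline values in the seven domains: 0 of 14. Weight is planned only as a baseline characteristic (SAP 7.2).

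**Step 3. Whether the stated reason explains the omission.** Early termination lowers n at later visits but does not erase earlier values. SAP 3.3 gives 1081 participants, and the schedule in SAP 3.7 has all seven domains assessed at Week 4. The last visit in the dropped analyses is Week 52, and Protocol 4 provides for people who had got that far: "Subjects who already completed participation through Week 52 in PTI-125-10 will have the option to return to the study and continue participation". Protocol 13 allows the sponsor to stop the study at any time, yet 12.2 makes no exception for that case.

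**Step 4. Whether the protocol version explains it.** SAP 1 says the SAP follows protocol version 3.0, dated 10-Nov-2023, and SAP 3.1 describes a 52-week design. The supplied protocol is a later text without the 52-week limit. Its summary of changes, as supplied, shows 12.3 revised and 12.4 to 12.6 added, but no change to 12.2. A version difference is therefore unlikely to account for the conflict.

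**Step 5. Listings.** SAP 9 and 12.3 cannot both stand with SAP 6.1.6, SAP 10 and Table 4. The first pair calls for listings of these data; the other three leave them out. The SAP does not say which prevails.

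**The case against.** The strongest reply has four parts.

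*The change is declared, and the SAP is not exclusive.* SAP 10 is the right place for a departure, and SAP 1 allows further analyses if the study report identifies them as unplanned. The study is single-arm, open-label and exploratory, so mean changes over time have no concurrent control. All of this is true and limits what the summaries can show. But disclosure does not reconcile SAP 10 with 12.2, and 12.2 promised description only.

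*Serious findings will surface elsewhere.* Protocol 7.1.9 says study drug should be discontinued for defined C-SSRS responses, and it makes a defined weight loss with low BMI a stopping criterion. Protocol 10 requires the reason for early discontinuation to be recorded, and SAP 7.1 summarises reasons for leaving the study. This stands as partial capture. It covers the more serious findings, and stopping drug is not always leaving the study.

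*The breach is narrower than it may look.* A reader might infer that all the dropped domains contravene Protocol 12.2. They do not: 12.2 names laboratory results and vital signs only. The C-SSRS and the examinations rest on Protocol 4, and no summary of weight or ECG is promised in either place.

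*Listings are not plainly removed.* A reader might also infer that the SAP settles against every listing of these data. That is the better reading of SAP 6.1.6, SAP 10 and Table 4, but SAP 9 and 12.3 say otherwise. Table 4 is also an imperfect inventory: SAP 9.1.4 promises a listing of all adverse events with the non-treatment-emergent ones flagged, whereas listing 16.2.7.1 is titled for treatment-emergent events. The supportable statement is that none is itemised and the text is inconsistent.

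**Conclusion.** The conflict is real and should be corrected before the report is written. For laboratory results and vital signs, SAP 10 contradicts Protocol 12.2 (8 scheduled summaries), and the reason given does not justify dropping values already collected. For the C-SSRS and the brief examinations (15 summaries), the SAP leaves unreported what Protocol 4 calls safety measures. For weight and ECG (8 summaries), reporting is advisable but was not promised. On listings, the defect is an internal contradiction.

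These figures count planned items. They do not measure the effect on any conclusion, because the documents do not give the number of participants with values at each visit. The verdict assumes that 12.2 read the same in version 3.0, inferred from the silence of the summary of changes, and that output titles describe their contents.

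A reader might infer that safety oversight during the study was weakened. The documents do not support that: SAP 1 and 4.2 describe a DSMB working under its own charter with separate outputs. Those outputs, however, do not put the results into the study report.

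**What to change.** 1. Restore descriptive change-from-Study-Day-1 summaries of laboratory results and vital signs for the visits actually collected, showing n at each visit. Add them to SAP 2.2.1 and to the table list in SAP 12.2.
2. Reconcile SAP 6.1.6, 9, 10 and 12.3 so that collected laboratory, vital-sign, brief-examination and C-SSRS data, and preferably weight and ECG, are at least listed. Counting the two examinations as one, that is 4 + 2 = 6 listings. Where a domain cannot be reported, SAP 10 should give a reason specific to it and the number of participants with post-baseline values.

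An optional extra, not part of the error, is a count of participants with liver-test values above the numeric thresholds already in Protocol 7.1.9. These should be labelled as laboratory values, not as stopping-criterion events, because the ALP criteria also require a judgement of liver origin and drug relationship.

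No new data collection or hypothesis test is needed. Because SAP 6.1.6 also restricts the CDISC datasets, some domains may need datasets built and data cleaned; the documents do not show their cleaning status. The report becomes longer.
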